2.14 Interim analysis

The primary endpoint analysis was performed after all subjects completed Week 16 or discontinued earlier in order to support regulatory filing.

The investigators, site personnel and monitors continue to remain blinded to the treatment each subject received at randomization until all patients have completed the study (Week 60 Follow-up) and the final database lock has occurred. Additional analyses may be performed to support interactions with health authorities, as necessary.

3 Sample size calculation

An overall type I error (2-sided) of 5% will be used to control type I error. Secukinumab i.v. regimen will be tested versus placebo with respect to the primary endpoint (ASAS40 response at Week 16). A sample size of 250 axSpA patients (200 AS patients and 50 nr-axSpA patients) per group is deemed appropriate to achieve adequate power for the primary and secondary endpoints for this study.

An ASAS40 response rate of about 28.2% for the AS population in the placebo group at week 16 was reported in a published phase III study (CAIN457F2320). The ASAS40 response to secukinumab 150 mg is estimated to be 44.9% in the AS population based on the lower bound of the 90% confidence interval of risk difference from the Meta-analysis of 3 phase III studies (CAIN457F2310, CAIN457F2320 and CAIN457F2308). With 250 patients per treatment group (200 AS patients and 50 nr-axSpA patients), there would be approximately 96% power to detect a treatment difference of 16.7% in ASAS40 response rates between secukinumab and placebo in the evaluation of the primary efficacy hypothesis at Week 16 (Chi Square test, NQuery 7.0). The overall sample size will be 500 patients (400 AS patients and 100 nr-axSpA patients) for a randomization ratio of 1:1.

The estimated power with the chosen sample size for secondary efficacy endpoints based on the pooled results of the same phase III studies (CAIN457F2310, CAIN457F2320 and CAIN457F2308) are summarized in Table 3-1 for binary endpoints and Table 3-2 for continuous endpoints.

Endpoint	Response Rate		Power
	Secukinumab(N = 200 AS + 50 nr-axSpA)	Placebo (N = 200 AS + 50 nr-axSpA)	_
ASAS 5/6	44.2%	19.5%	99%
ASDAS-CRP major improvement	27.8%	6.4%	99%
ASAS20	59.0%	38.4%	99%
ASDAS-CRP inactive disease	13.6%	3.5%	97%
ASAS partial remission	15.2%	5.5%	92%

Table 3-1 Summary of power for binary secondary endpoints

Novartis	Confidential	Page 28 of 45
SAP		Study No. CAIN457P12301

Table 3-2	Summary of power for continuous endpoints			
Endpoint	Mean change	Mean change from baseline		Power
	Secukinumab(N = 200 AS + 50 nr- axSpA)	Placebo (N = 200 AS + 50 nr- axSpA)	standard deviation	
hsCRP ¹	-0.79	0.09	0.867	99%
BASDAI	-2.61	-1.48	2.241	99%
BASFI	-2.14	-1.13	2.253	99%
SF-36 PCS	6.87	3.99	6.898	99%
ASQoL	-4.46	-2.56	4.714	99%
PSQI ²	-1	0	3.9	81%

¹ hsCRP is in log scale

² Source: mean change from baseline is from Karatas et al 2018 (AS study, median was used) and common standard deviation is from Taylor-Gjevre et al 2011 (RA study, largest standard deviation was used).

4 Change to protocol specified analyses

No change from protocol specified analysis was made.

5 Appendix

5.1 **Description of efficacy variables**

Assessment of Spondyloarthritis International Society criteria (ASAS) response criteria

The ASAS response measures consist of the following assessment domains (Sieper 2009)

Main ASAS domains:

- 1. Patient's global assessment of disease activity measured on a VAS scale
- 2. Patient's assessment of back pain, represented by either total or nocturnal pain scores, both measured on a VAS scale. For ASAS response analyses, the total back pain will be used.
- 3. Function represented by BASFI average of 10 questions regarding ability to perform specific tasks as measured by VAS scale
- 4. Inflammation represented by mean duration and severity of morning stiffness, represented by the average of the last 2 questions on the 6-question BASDAI as measured by VAS scale (at least one question is needed)

Additional assessment domains:

2. C-reactive protein (acute phase reactant)

ASAS40

Novartis	Confidential	Page 29 of 45
SAP		Study No. CAIN457P12301

The ASAS40 response is defined as a $\ge 40\%$ improvement and an ≥ 2 units on a scale of 10 in at least three of the following 4 domains: back pain, patient global assessment of disease activity, physical function (BASFI) and inflammation (mean score of items 5 and 6 of the BASDAI) without any worsening in the remaining domain.

ASAS20

The ASAS20 response is defined as an improvement of $\ge 20\%$ and ≥ 1 unit on a scale of 10 in at least three of the four main domains and no worsening of $\ge 20\%$ and ≥ 1 unit on a scale of 10 in the remaining domain.

ASAS 5/6

The ASAS 5/6 improvement criteria is an improvement of $\geq 20\%$ in at least five domains.

ASAS partial remission

The ASAS partial remission is defined as a value not above 2 units in each of the four main domains on a scale of 10.

ASDAS-CRP, ASDAS Inactive disease, clinically important and major improvement

The ASDAS-CRP (Ankylosing Spondylitis Disease Activity Score) will be utilized to assess the disease activity status. Parameters used for the ASDAS include: total back pain (BASDAI question 2), the patient global assessment of disease activity (ASAS component 1), peripheral pain/swelling (BASDAI question 3), duration of morning stiffness (BASDAI question 6) and C-reactive protein (CRP) in mg/liter (CRP) (CRP) (CRP) (CRP) (CRP) (CRP)) (Sieper 2009, Lukas 2009).

The ASDAS formulas are as follows:

ASDAS-CRP = $0.121 \times \text{total back pain} + 0.110 \times \text{patient global} + 0.073 \times \text{peripheral pain/swelling} + 0.058 \times \text{duration of morning stiffness} + 0.579 \times \ln(\text{CRP} + 1)$

CRP is in mg/liter, $\sqrt{100}$; the range of other variables is from 0 to 10; ln represents the natural logarithm; $\sqrt{100}$ represents the square root. If any of the ASDAS components are missing, ASDAS will not be calculated.

Disease activity states: inactive disease, moderate disease activity, high disease activity, and very high disease activity. The 3 values selected to separate these states are < 1.3 between inactive disease and moderate disease activity, < 2.1 between moderate disease activity and high disease activity, and > 3.5 between high disease activity and very high disease activity. Selected cutoffs for improvement scores are a change \geq 1.1 unit for "minimal clinically important improvement" and a change \geq 2.0 units for "major improvement" (Machado 2011). Separate states will be calculated for ASDAS-CRP

Novartis	Confidential	Page 30 of 45
SAP		Study No. CAIN457P12301

ASAS components

Patient's global assessment of disease activity (VAS)

The patient's global assessment of disease activity will be performed using a 100 mm visual analog scale (VAS) ranging from not severe to very severe, after the question *"How active was your disease on average during the last week?"*.

Patient's assessment of total back pain and nocturnal back pain intensity (VAS)

The patient's assessment of back pain will be performed using a 100 mm VAS ranging from no pain to unbearable pain, after the question "Based on your assessment, please indicate what is the amount of back pain at any time that you experienced during the last week?" and "Based on your assessment, please indicate what is the amount of back pain at night that you experienced during the last week?".

Bath Ankylosing Spondylitis Functional Index (BASFI)

The BASFI is a set of 10 questions designed to determine the degree of functional limitation in those subjects with AS. The ten questions were chosen with a major input from subjects with AS. The first 8 questions consider activities related to functional anatomy. The final 2 questions assess the subjects' ability to cope with everyday life. A 100 mm VAS is used to answer the questions. The mean of the ten questions gives the BASFI score – a value between 0 and 10. In the case that some of the BASFI questions are missing, then the average of the non-missing items is used (Braun 2009, van Tubergen 2001).

Bath Ankylosing Spondylitis Disease Activity Index (BASDAI)

The gold standard for measuring and evaluating disease activity in AS is the BASDAI. The BASDAI consists of a 0 through 10 scale (0 being no problem and 10 being the worst problem), which is used to answer 6 questions pertaining to the 5 major symptoms of AS:

- 1. Fatigue
- 2. Spinal pain
- 3. Joint pain / swelling
- 4. Areas of localized tenderness
- 5. Morning stiffness severity
- 6. Morning stiffness duration

To give each symptom equal weighting, the mean (average) of the two scores relating to morning stiffness is taken and is then added to the sum of the first 4 questions. The resulting 0 to 50 score is divided by 5 to give a final 0 - 10 BASDAI score. Scores of 4 or greater suggest suboptimal control of disease, and subjects with scores of 4 or greater are usually good candidates for either a change in their medical therapy or for enrollment in clinical trials evaluating new drug therapies directed at. BASDAI is a quick and simple index taking between 30 secs and 2 mins to complete. At least 4 questions should be non-missing to calculate the BASDAI score. Otherwise, BASDAI score will be missing (Haywood 2002). If both Q5 and Q6 are missing or one of Q1 to Q4 is missing, then the total sum should be divided by 4 instead

Novartis	Confidential	Page 31 of 45
SAP		Study No. CAIN457P12301

of 5. If two of Q1 to Q4 is missing and both Q5 and Q6 are not missing, then the sum should be divided by 3.

High Sensitivity C-reactive protein (hsCRP)

This assessment will be performed in order to identify the presence of inflammation, to determine its severity and to monitor the response to treatment.

Novartis SAP	Confidential	Page 32 of 45 Study No. CAIN457P12301		

Novartis SAP	Confidential	Page 34 of 45 Study No. CAIN457P12301

5.2 Description of health-related quality of life variables

Ankylosing Spondylitis Quality of Life (ASQoL)

The ASQoL is a self-administered questionnaire designed to assess health-related quality of life in adult patients with Ankylosing Spondylitis. The ASQoL contains 18 items with a dichotomous yes/no response option. A single point is assigned for each "yes" response and no points for each "no" response resulting in overall scores that range from 0 (least severity) to 18 (highest severity). As such, lower score indicates better quality of life. Items include an assessment of mobility/energy, self-care and mood/emotion. The recall period is "at the moment," and the measure requires approximately 6 minutes to complete.

At least 15 answered questions are required to be able to calculate ASQoL using mean imputation, (sum of answered)/(number answered)*18 (Doward 2003).

SF-36

The Short Form Health Survey (SF-36) is a widely used and extensively studied instrument to measure health-related quality of life among healthy subjects and patients with acute and chronic conditions. It consists of eight subscales (domains) that can be scored individually: Physical Functioning, Role-Physical, Bodily Pain, General Health, Vitality, Social Functioning, Role-Emotional, and Mental Health. Two overall summary scores, the Physical Component Summary (PCS) and the Mental Component Summary (MCS) also can be computed. The SF-36 has proven useful in monitoring general and specific populations, comparing the relative burden of different disease, differentiating the health benefits produced by different treatments, and in screening individual patients. The eight domains are based on a scale from 0-100 while PCS and MCS are norm-based scores with a mean of 50 and a standard deviation of 10.

Quality metric uses weighted maximum likelihood estimation, a modified version of item response theory (IRT) to estimate scale scores when a respondent is missing multiple items. The PCS summary score measure requires scores for seven scales, one of which must be the PF scale and the MCS score also requires scores for seven scales, one of which must be the MH scale. Only one item is needed for each of the multi-item domains.

Novartis SAP	Confidential	Page 36 of 45 Study No. CAIN457P12301

Novartis SAP	Confidential	Page 37 of 45 Study No. CAIN457P12301

Pittsburgh Sleep Quality Index (PSQI)

The Pittsburgh Sleep Quality Index is a self-report questionnaire that assesses sleep quality over a 1-month time interval. Consisting of 19 items under 9 questions, the PSQI measures several different aspects of sleep, offering seven component scores and one composite score. The component scores consist of subjective sleep quality (1 item), sleep latency (2 items, i.e., how long it takes to fall asleep), sleep duration (1 item), habitual sleep efficiency (3 items, i.e., the percentage of time in bed that one is asleep), sleep disturbances (9 items), use of sleeping medication (1 item), and daytime dysfunction (2 items).

Of the 19 items, items 1-4 have free entry responses asking for usual bedtime and wake up time, number of minutes to fall asleep, and hours slept per night. Items 5-17 have 4-point Likert scale responses relating to frequency of specified sleep problems. Item 18 has a 4-pont Likert scale response relating to overall assessment of sleep quality ("very good", "fairly good", "fairly bad", or "very bad"). Item 19 has a 4-point Likert response scale relating to respondent's overall

Novartis	Confidential	Page 38 of 45
SAP		Study No. CAIN457P12301

assessment of "enthusiasm to get things done" ("no problem at all", "only a very slight problem", "somewhat of a problem", or "a very big problem").

Each item is weighted on a 0-3 interval scale. In scoring the PSQI, seven component scores are derived, each scored 0 (no difficulty) to 3 (severe difficulty). The global PSQI score is then calculated by totaling the seven component scores, providing an overall score ranging from 0 to 21, where lower scores denote a healthier sleep quality and higher scores indicate worse sleep quality.

Questions 1 through 9 are not allowed to be missing. If these questions are missing then any scores calculated using missing questions are also missing.

5.3 Visit Windows

Baseline and post-baseline definitions

In general, a *baseline* value refers to the last measurement made prior to administration of the first dose of study treatment. A *post-baseline* value refers to a measurement taken after the first dose of study treatment.

Analysis visit windows

Analysis visit windows will be used for the data that is summarized by visit; they are based on the study visit and evaluation schedule and comprise a set of days around the nominal visit day. For any assessment, there are protocol defined scheduled visits around which analysis visit windows were created to cover the complete range of days within the study.

When visit windows are used, all visits will be re-aligned, i.e., they will be mapped into one of the visit windows. E.g., if the *Week 4* visit of a subject is delayed and occurs on Day 46 instead of on Day 29, it will be re-aligned to visit window *Week 8*. In the case of major deviations from the visit schedule, or due to unscheduled visits, several assessments of a subject may fall in a particular visit window (either scheduled or unscheduled). Statistical approaches to handle multiple assessments in a given visit window are specified below.

Of note, subjects are allowed to have gaps in visits. All data collected will be displayed in listings.

Study No. C.

Analysis Visit	Target Day	Analysis Visit Window	Group 1	Group 2	Group 3	Group 4	Group 5	Group 6	Group 7	Group 8	Group 9	Group 10	Group 11	Group 12	Group 13
Baseline	1	≤ 1	≤ 1	≤ 1	≤ 1	≤ 1	≤ 1	≤ 1	≤ 1	≤ 1	≤ 1	≤ 1	≤ 1	≤ 1	≤ 1
Week 4	29	2-43	2-43	2-43			2-43	2-43	2-43	2-43	2-43	2-43	2-43		
Week 8	57	44-71	44-71	44-71	2-85		44-71	44-71	44-71	44-71	44-71	44-71	44-85		
Week 12	85	72-99	72-99	72-99			72-99	72-99	72-99	72-99	72-99	72-99			
Week 16	113	100-127	100-127	100-127	86-141	2-141	100-127	100-127	100-141	100-141	100-127	100-127	86-141	2-239	2-239
Week 20	141	128-155	128-155	128-155			128-239	128-155			128-155	128-155			
Week 24	169	156-173	156-183	156-183	142-267	142-267		156-197	142-197	142-197	156-183	156-183	142-253		
Week 25	176	174-187											**		
Week 28	197	188-211	184-211	184-211							184-211	184-211			
Week 32	225	212-239	212-239	212-239				198-253	198-253	198-253	212-239	212-239			
Week 36	253	240-267	240-267	240-267							240-267	240-267			
Week 40	281	268-295	268-295	268-295				254-323	254-323	254-323	268-295	268-295			
Week 44	309	296-323	296-323	296-323							296-323	296-323			
Week 48	337	324-351	324-351	324-351			240-351				324-351	324-379	***		
Week 52	365	352-393	324-393	352-435	268-435	268-435	352-435	324-393	324-393	324-393	352-393		352-393	240-393	240-435
Week 60	421	394-435	394-435					394-435	394-435	394-435	394-435	380-435	394-435	394-435	
Group 1: F	Patient's g	global asses	sment of d	lisease act	ivity (VAS),	Patient's a	assessmen	t of back p	ain intensit	y (VAS), B	ASFI, BAS	DAI, Vital s	signs		
Group 3: S	SF-36, AS	SQoL,	,			Lipids	5								
Group 4:		, , Ca	ardiovascul	ar panel											
Group 5:	, PSC	QI,													
Group 7: h	ISCRP														

Table 5-4Analysis visit windows

Novartis

SAP

\sim	C		
Co	nfic	len	tial

Page 40 of 45 Study No. CAIN457P12301

Analysis Visit	Target Day	Analysis Visit Window	Group 1	Group 2	Group 3	Group 4	Group 5	Group 6	Group 7	Group 8	Group 9	Group 10	Group 11	Group 12	Group 13
Group 8: h	nematolog	gy, blood ch	emistry, ur	inalysis											
Group 9: l	Jrine preg	gnancy test													
Group 10:	Weight														
Group 11:	PK														
* The first day of administration of randomized study treatment (first dose) is defined as Day 1.															
** For Week 25 visit window, if the patient visited at week 24, then any visit at day range between 7-14 days after week 24 visit will be counted as Week 25; Otherwise, if the patient missed the visit of week 24, please use the range of 254-267 to count the visit into week 25.															
*** For We	*** For Week 48 visit window, if the patient visited week 25 as defined above, then any day after week 25 visit up to day 351 would be counted as Week 48.														

Novartis

SAP

Novartis	Confidential	Page 41 of 45
SAP		Study No. CAIN457P12301

The following rules are used to determine the window for an applicable visit post baseline: "Lower limit" = "upper limit of prior applicable visit" + 1. "Upper limit" = "target day of current visit" + integer part of ("target day of next applicable visit" – "target day of current visit")/2. Lower limit of the first applicable visit is always Day 2.

The mapping described above applies to all visits (not just scheduled visits). Repeat and/or unscheduled visits (which will be numbered in the database according to new NCDS standards) will be mapped for analysis purposes in the same way as scheduled visits. This leaves the possibility, then, for multiple measurements within an analysis window. The following conventions will be used to determine the appropriate measurement to be summarized in the event of multiple measurements within a visit window.

Timing of measurement Type of data Rule Baseline All data The last measurement made prior to administration of the first dose of study treatment - note this may include measurements taken on the day of randomization (e.g., lab). Baseline assessments scheduled for and captured on Day 1 will be considered baseline measurements regardless of the time of assessment. If a patient did not receive any dose of study treatment then the randomization date will be used. Only the date part will be considered if there is only one assessment on Day 1 but if there are multiple assessments on Day 1, then the following rules will apply: 1. If time of assessment exist, select the last available measurement prior to the reference start date/time considering time if no measurement prior to the reference start date/time then considering time select the earliest measurement post reference start date/time 2. If time of assessment does not exist the measurement from the lowest CRF visit number will be used. Post-baseline efficacy All data The measurement closest to the target day will be used. In the event two measurements are taken equally apart (e.g., 1 day before target date and 1 day after) the first one will be used. If the patient switches from placebo to AIN within the window the following rules apply: If the analysis visit window is ≤ week 16, then 1 If available, the closest measurement to the target date which is on or before the switch date will be used If there are no data on or before the switch then the closest measurement after the switch to target will be used If the analysis visit window is > week 16, then 2 If available, the closest measurement to the target date which is after the switch date will be used If there are no data after the switch then the closest to target before or on the switch date will be use Cases where the same parameter is recorded more than once on the same date will be handled as follows: If time of completion exists the earliest measurement will be use If time does not exist the measurement from the lowest CRF visit number will be used Post-baseline safety Summary visit The measurement closest to the target day will be used. In the event two information (e.g., measurements are taken equally apart (e.g., 1 day before target date and 1 lab, etc.) day after) the first one will be used. If the patient switches from placebo to AIN within the window the following rules apply: If the analysis visit window is ≤ week 16, then 1

Table 5-5 Rules for flagging variables

Timing of measurement	Type of data	Rule
		 If available, the closest measurement to the target date which is on or before the switch date will be used
		 If there are no data on or before the switch then the closest measurement after the switch to target will be used
		2. If the analysis visit window is > week 16, then
		 If available, the closest measurement to the target date which is after the switch date will be used
		 If there are no data after the switch then the closest to target before or on the switch date will be use
		Cases where the same parameter is recorded more than once on the same date will be handled as follows:
		If time of completion exists the earliest measurement will be used
		 If time does not exist the measurement from the lowest CRF visit number will be used
		 If CRF visit number is the same the average value will be used
Post-baseline safety	Notable abnormalities (e.g., lab)	The most extreme measurement in the window will be used. Note this means a patient can have a notably high and notably low measurement within a window

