2.1 Data analysis general information

To support the submission, tables and figures will be generated for overall axSpA population. Listings will be generated for overall axSpA population and will be sorted by disease condition (AS and nr-axSpA), except for the listing of randomization allocation to treatment which will be sorted by the randomization number.

Summary statistics for continuous variables will include N, mean, standard deviation, minimum, lower quartile, median, upper quartile and maximum. Summary statistics for discrete variables will be presented in the number and percent of subjects in each category.

Data analyses will be presented by treatment regimen. Efficacy and safety data for the placebocontrolled period (or the entire treatment period as appropriate) will be presented by the following 2 treatment groups. Subjects may be included in more than one treatment group for some analyses (e.g., exposure-adjusted adverse events over the entire treatment period). The 2 treatment groups represent the regimens subjects will be eligible to be randomized to for the first 16 weeks of the study.

- Secukinumab regimen: approximately 200 AS subjects and approximately 50 nr-axSpA subjects; These subjects will receive secukinumab 6 mg/kg i.v. at randomization (Baseline (BSL) visit), followed by the administration of secukinumab 3 mg/kg i.v. every four weeks starting at Week 4 through Week 48 (exposure through Week 52).
- Placebo regimen: approximately 200 AS subjects and approximately 50 nr-axSpA subjects; These subjects will receive i.v. placebo at randomization (BSL visit), Weeks 4, 8, and 12, followed by the administration of secukinumab 3 mg/kg i.v. at Week 16 and every four weeks through Week 48 (exposure through Week 52).

Note that the treatment groups above for a subject may differ depending on the time period of the analysis and whether one assesses the subject for efficacy or safety.

Comparative efficacy data

Comparative efficacy analyses (i.e., inferential efficacy comparisons with placebo) will focus on the time period when both active drug and the placebo are given in a manner suitable for making comparisons (e.g., double-blind). For AIN457P12301, this is the first 16-weeks of treatment. Comparative efficacy will be performed based on the Full Analysis Set (FAS) population using the randomized treatment. Data collected after Week 16 will generally be summarized descriptively on the FAS population using treatment sequence.

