2.9 Pharmacokinetic endpoints

During modeling of the PK of secukinumab, the broad principles outlined in the [FDA Guidance for Industry: Population Pharmacokinetics] will be followed.

All completed subjects with quantifiable pharmacokinetic (PK) measurements will be included in the PK data analysis. Serum concentrations will be expressed in mass per volume units. All concentrations below the limit of quantification as well as missing data will be labeled as such in the concentration data listings. PK concentrations will be summarized by visit and treatment group. In addition to mean, standard deviation (SD), coefficient of variation (CV), median and quartiles, the geometric mean and geometric coefficient of variation (CV), minimum and maximum, as well as n and n(log) will be presented. The formula for deriving the geometric mean and CV (%) is as follows:

- CV(%) = (SD/mean)*100,
- geometric mean=exp((sum of log transformed data) / number of non-missing data points after log transformation),
- geometric CV = sqrt(exp(variance of log-transformed data)-1)*100.

In addition, sample number, concentration, sample date, sample time and elapsed time from first dose (in days) will be listed by treatment sequence.

Values below lower limit of quantification/below detection limit will be imputed by 0.

Novartis	Confidential	Page 23 of 45
SAP		Study No. CAIN457P12301

Pharmacokinetic data of the study treatment will be analyzed with a populationpharmacokinetic mixed effects model. The analysis will be based on a pooled data set, including PK samples from previous studies. The modeling approach will be further detailed in a modeling plan. Results will be reported separately.

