2.11 Patient reported outcomes (PROs)

Patient reported outcomes will be evaluated based on FAS unless otherwise specified.

BASDAI

The following variables will be evaluated:

• BASDAI

For BASDAI, summary statistics of observed data by visit and change from baseline in BASDAI will be provided for each treatment.

BASFI

See Section 5.1 Description of efficacy variables for details.

Patient's global assessment of disease activity (VAS)

Summary statistics of observed data by visit and change from baseline in patient's global assessment of disease activity will be provided for each treatment.

Patient's assessment of back pain intensity (VAS)

Summary statistics of observed data by visit and change from baseline in patient's assessment of back pain intensity will be provided for each treatment.

SF-36

The following variables will be evaluated:

- SF-36 domain scores (based on a scale of 0-100)
- SF-36 PCS (norm-based scores)
- SF-36 PCS (improvement of ≥ 2.5 points, Lubeck 2004)

For the change from baseline in SF-36 summary scores (PCS), summary statistics will be provided using observed data for each treatment regimen.

For the responder analyses, the proportion of responders will be descriptively summarized along with its 95% CI for each randomized treatment based on observed data.

The SF-36 domain scores will be summarized by treatment.

ASQoL

Summary statistics of observed data by visit and change from baseline in ASQoL will be provided for each treatment.

Novartis SAP	Confidential	Page 26 of 45 Study No. CAIN457P12301

PSQI

Summary statistics of observed data by visit and change from baseline in PSQI score will be provided for each treatment.

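### SAP Table 5-4 has window errors after Week 16: Group 1 Week 52 overlaps Week 48, the Week 25 efficacy measures have no cell in their own group, and the PK footnotes misplace Weeks 25 and 48

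*SAP*

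**What the plan says.** SAP 5.3 builds each post-baseline window from a written rule. The lower limit is one day after the "upper limit of prior applicable visit". The upper limit is the visit's own target day plus the integer part of half the gap to the next applicable visit. The section also says that each visit is mapped into one window and that unscheduled visits are mapped in the same way. When several efficacy values fall in one window, Table 5-5 says: "The measurement closest to the target day will be used".

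The cells of Table 5-4 that matter here are:

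| Visit | Target day | Generic column | Group 1 | Group 9 | PK (Group 11) |
|---|---|---|---|---|---|
| Week 24 | 169 | 156-173 | 156-183 | 156-183 | 142-253 |
| Week 25 | 176 | 174-187 | blank | blank | two-star footnote |
| Week 28 | 197 | 188-211 | 184-211 | 184-211 | none |
| Week 48 | 337 | 324-351 | 324-351 | 324-351 | three-star footnote |
| Week 52 | 365 | 352-393 | 324-393 | 352-393 | 352-393 |

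The two-star footnote counts a PK visit 7 to 14 days after the Week 24 visit as Week 25, and adds: "Otherwise, if the patient missed the visit of week 24, please use the range of 254-267 to count the visit into week 25". The three-star footnote says that, for a subject with a Week 25 visit so defined, "any day after week 25 visit up to day 351 would be counted as Week 48".

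These windows feed by-visit tables. For BASDAI, SAP 2.11 says "summary statistics of observed data by visit and change from baseline in BASDAI will be provided for each treatment". For PK, SAP 2.9 says "PK concentrations will be summarized by visit and treatment group".

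On the protocol side, Table 8-1 marks patient global, back pain, BASFI and BASDAI at all 16 visits from Baseline to Week 60, including Week 25. Section 4.1 gives the efficacy measures and PK sample of that visit a purpose: response between two doses and its relation to concentration. Table 8-6 schedules PK sample 10 at Week 25, and nothing between then and Week 48.

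**The concern.** A window table should give every scheduled assessment a place and every day one label. Table 5-4 fails on both counts after Week 16. Some days belong to two or three visits. One scheduled efficacy visit has no cell in its own group. One PK range is labelled with a visit that took place about three months earlier. Programmers have to code this table, and two of them working independently could produce different summaries. At stake are the descriptive results at Weeks 24, 25, 48 and 52, among them the Week 25 data that the protocol collects for a stated reason.

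**Working it through.** **Inputs.** Target days, printed windows, rule and footnotes are from SAP 5.3. Scheduled assessments are from protocol Tables 8-1 and 8-6. The last upper limit, Day 435, is taken as given.

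**Does the rule reproduce the table?** Mostly. Outside PK there are 101 legible group cells and 100 agree. The exception is Group 1 Week 52. The generic column has 15 cells; 12 agree, and the three around Week 25 are one day off. Every window up to Week 16 agrees in every column.

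**1. Group 1, Week 52**
- Week 48 upper limit: 337 + int((365 - 337)/2) = 337 + 14 = 351.
- Week 52 lower limit: 351 + 1 = 352. Upper limit: 365 + int((421 - 365)/2) = 365 + 28 = 393.
- The rule gives 352-393, as in the generic column and Group 9. The printed cell is 324-393.
- Overlap: 351 - 324 + 1 = 28 days.
- The value 324-393 is correct for Groups 6 to 8, which go from Week 40 to Week 52: 281 + int((365 - 281)/2) = 323, so Week 52 starts at 324. A copying slip is plausible.
- Consequence: a value from Days 324-351 can stand in for Week 52 when nothing nearer Day 365 exists. For example, a subject who stops after a Day 309 dose (Week 44) has the end-of-treatment visit four weeks later, on Day 337, which lies in both windows.

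**2. Week 25 efficacy measures**
- Without Week 25, the rule gives Week 24 an upper limit of 169 + int(28/2) = 183 and Week 28 the range 184-211. These are the printed Group 1 cells, so they are consistent with the rule; the scheduled visit was left out.
- A Day 176 value therefore sits in Week 24. It is 7 days from that target, so an on-time Day 169 value is used instead. If Week 24 was missed, the Day 176 value is reported as Week 24.
- With Week 25 included: Week 24 ends at 169 + int(7/2) = 172, Week 25 ends at 176 + int(21/2) = 186, and Week 28 starts at 187. The rule gives 156-172, 173-186 and 187-211, against 156-173, 174-187 and 188-211 in the generic column.

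**3. PK**
- Fallback range: 254 - 176 = 78 and 267 - 176 = 91 days after the Week 25 target. The closest scheduled visit is Week 36 (Day 253), which has no PK draw.
- If Week 24 was missed, a sample on Day 176 falls in 142-253 and is labelled Week 24.
- Such a subject has no Week 25 visit as the footnote defines it, unless a sample falls on Days 254-267. Without one, the three-star footnote states no Week 48 window, so the scheduled Day 337 samples are unassigned. The same holds for anyone who attended Week 24 but not Week 25.
- With visits on Days 169 and 176, Week 24 is 142-253, Week 25 is 176-183 and Week 48 is 177-351. Day 176 has two labels, Days 177-183 have three and Days 184-253 have two: 1 + 7 + 70 = 78 days with more than one label.
- With Week 25 as an applicable visit, the rule gives Week 24 = 142 to 169 + int(7/2) = 172; Week 25 = 173 to 176 + int(161/2) = 256; Week 48 = 257-351.

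**The case against.** The strongest reply is that the overlaps need not count anything twice. SAP 5.3 says each visit goes into one window, and the footnotes can be read as exceptions to the 142-253 cell. This stands: the overlaps are ambiguities, and a reader who infers that values are counted in two summaries goes beyond the text. But the SAP does not say which label wins.

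Second, the PK overlap is mostly remote. No draw is scheduled between Weeks 25 and 48, so it matters mainly for off-schedule samples, which Table 8-6 does foresee. SAP 2.9 also restricts the PK analysis to completed subjects. This stands for the overlap. It does not answer the missing Week 48 window or the 254-267 label.

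Third, a Week 25 window does exist, in the generic column. True, so it would be wrong to say that the table has none; it is not carried into Group 1. The efficacy-concentration analysis may also sit in a redacted section or in the separate modelling plan, and listings keep all data. One therefore cannot infer that the Week 25 data are lost to every analysis.

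Fourth, the wide Week 52 cell might be meant to catch early end-of-treatment visits. Nothing in the SAP says so, and Group 9 does not do it.

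**Conclusion.** The errors hold on the SAP's own rule, table and footnotes, and the point is minor. Its size is a 28-day overlap in Group 1 Week 52, a missing Week 25 cell for four efficacy measures, a PK fallback 78 to 91 days off target, and no stated Week 48 PK window for subjects without a Week 25 visit. The documents do not say how many subjects are affected.

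A reader might infer that the primary or secondary tests are in doubt. The documents do not support that. Protocol section 12 limits inferential comparisons with placebo to the first 16 weeks, and this SAP does not rerun the Week 16 analyses. For later data it says: "Data collected after Week 16 will generally be summarized descriptively on the FAS population using treatment sequence". The visible effect is on by-visit summaries of BASDAI, BASFI, back pain, patient global, vital signs and PK. Redacted sections cannot be checked, so it cannot be shown that nothing else uses these windows.

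The Group 1 consequences rest on the closest-to-target rule. Table 5-5 does not name PK, so how PK values are chosen within a window is open.

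**What to change.** 1. Set Group 1 Week 52 to 352-393.
2. Give patient global, back pain, BASFI and BASDAI the windows 156-172, 173-186 and 187-211 for Weeks 24, 25 and 28, and align the generic column. Alternatively, keep 156-173, 174-187 and 188-211 and amend the written rule. Leave vital signs at 156-183 and 184-211 unless they are scheduled at Week 25.
3. For PK, delete the 254-267 fallback and treat Week 25 as an applicable visit: Week 24 = 142-172, Week 25 = 173-256 and Week 48 = 257-351 for all subjects. Where Week 24 was attended, the 7-14 day anchor may stay, to separate Week 25 from Week 24 samples. State that each sample has one label, and how a value is chosen within a window.

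The cost is a few cells, two footnotes and possibly a separate group for vital signs. Subjects without a true Week 52 assessment no longer contribute a value from the Week 48 window to the Week 52 summary. The rule-based PK Week 25 window is wide, ending 256 - 176 = 80 days after target. Unlike the fallback it contains the target day, but an off-schedule sample could still be labelled Week 25. No endpoint, test or sample size changes.
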